Our primary outcome measure for this secondary objective will include fecal calprotectin and circulating levels of inflammatory cytokines as biomarkers of systemic inflammation. The sample size provides >80% power, at a threshold of alpha=0.05, for the detection of a 25% difference in marker changes in response to XN between the healthy adults in the Phase 1 trial and participants in this trial. Additionally, we will measure changes in Crohn's Disease Activity Index (CDAI) score for participants at each clinical visit to first determine eligibility and, second, compare end results to baseline for any change in score. Finally, results will be compared to the previous Phase 1 trial in healthy adults.

Aim 3. Collect samples and measure XN metabolism, gut permeability and impact on the microbiota.

We will assess XN metabolism, gut permeability and impact on the microbiota. Thus, our outcome measures for this objective include microbiota profiles, XN metabolites and bile acid metabolites.

Aim 4. (Exploratory) Generate a computational, theoretical model for assessing and understanding of the interactions between XN and the gut microbiome, and how the identified interactions may mitigate CD.

We will measure biomarkers of gut inflammation and gut integrity, and composition of intestinal microbiome species through various methods including measurement of circulating plasma endotoxin, CD14, intestinal fatty acid-binding protein, lipopolysaccharide-binding protein; lipidomic profiling; and TLR2/TLR4 activation.

8 Trial design

The design will be a triple-masked, randomized, placebo-controlled trial. Upon confirmation of eligibility and documentation of informed consent, those participants still interested and eligible to participate will be randomized to either: XN (24 mg/day plus 288 mg of rice protein plus 117.9 mg of excipients) or placebo (rice protein 288 mg/day plus117.9 mg of excipients) taken by mouth once daily for 8 weeks.

Methods Participants, interventions and outcomes

9 Study Setting

The clinical study will take place at an academic medical center, the National University of Natural Medicine's Helfgott Research Institute in Portland, OR, USA.

10 Eligibility criteria

Crohn's Disease (n=32):

Inclusion criteria

- Adults 21-70 years of age
- Active Crohn's disease not in remission based on a CDAI score >150
- Willing to take isolated Xanthohumol as a dietary supplement for 8 weeks

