A sample size of 12 per group provides 80% power to detect a 50% difference in proportions of participants between groups by chi2 test experiencing a laboratory abnormality or adverse event at a significance threshold of α =0.05. In addition, based on our preliminary trial data for change in TNF- α , and applying a 2-sided t-test of means, n=24 allows for n=12 per arm and provides >90% power, at a significance threshold α =0.05, to detect a mean change of -0.5 =/- 0.25 pg/ml in XN-treated participants with CD, based on an estimated mean change of 0.1 +/- 0.25 pg/ml from placebo. Will we randomize up to 32 participants to allow for attrition up to 25% [resulting in a final sample of at least n=24/arm.

Based on our preliminary trial data for change in TNF- α , and applying a 2-sided t-test of means, n=24 allows for n=12 per arm and provides >90% power, at a significance threshold α =0.05, to detect a mean change of -0.5 =/- 0.25 pg/ml in XN-treated participants with CD, based on an estimated mean change of 0.1 +/- 0.25 pg/ml from placebo. Will we randomize up to 32 participants to allow for attrition up to 25% [though we had <10% attrition in our previous trial in this population] resulting in a final sample of at least n=24/arm.

15 Recruitment

Participants will be recruited from the region via posted fliers and the NUNM clinic via posted fliers and IRB-approved mailings to current patients. Members of the study team will present information about study participation to CD support and community groups and set out flyers for attendees to pick up. In addition, we will use Craigslist and social media (i.e. Facebook and Instagram) as well as the NUNM weekly newsletter. Candidates from the community would

simply respond to a dedicated study telephone line or email, and express their interest, and are then contacted by a Study Coordinator.

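### Aim 2's claim of more than 80% power for a 25% difference from Phase 1 healthy adults cannot be reproduced from the protocol's figures, and it powers a cross-trial contrast instead of XN versus placebo

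*Protocol*

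**What the plan says.** Section 7, Aim 2, names fecal calprotectin and circulating cytokines as the main measures for this secondary objective. It then states: "The sample size provides >80% power, at a threshold of alpha=0.05". The effect to be detected is put in the words "for the detection of a 25% difference in marker changes in response to XN between the healthy adults in the Phase 1 trial", with this trial's participants as the other side of the comparison. No mean, SD, Phase 1 group size or sidedness accompanies the claim. For CDAI, the same aim says it will "compare end results to baseline for any change in score", and it ends by announcing a comparison with the Phase 1 trial.

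Section 14 holds the only numerical marker assumptions. "applying a 2-sided t-test of means", it plans "to detect a mean change of -0.5 =/- 0.25 pg/ml in XN-treated participants with CD". The other side of that calculation is "based on an estimated mean change of 0.1 +/- 0.25 pg/ml from placebo". Section 14 also says that "n=24 allows for n=12 per arm and provides >90% power". Up to 32 participants are randomised, with up to 25% attrition allowed.

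Section 8 describes a randomised, placebo-controlled trial. Section 20a makes Cohen's d between XN and placebo the principal assessment of the cytokines, with baseline to week 8 as the main interval. It gives no method for comparing this trial with Phase 1.

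**The concern.** There are two problems with one sentence.

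- **The number.** A 25% relative difference in a change of 0.5 pg/ml is small against an SD of 0.25. With 12 to 16 participants on XN, power of 80% looks out of reach.
- **The contrast.** The sentence compares patients with Crohn's disease in this trial with healthy adults in another. That comparison is not randomised. Disease status is inseparable from trial, period and conduct, so a difference would not show whether XN works in Crohn's disease. Hypothesis 2 in section 7 asks whether XN improves biomarkers and CDAI, and the concurrent placebo arm is there to answer it.

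A reader of Aim 2 would think the trial well powered for a modest effect. On the protocol's own figures it is powered only for a large one, and on a different contrast.

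**Working it through.** **Inputs (section 14, reading the plus-or-minus figure as an SD).** XN change -0.5 pg/ml; placebo change 0.1 pg/ml; SD 0.25 in each; 12 evaluable or 32/2 = 16 randomised per arm; two-sided alpha 0.05. Aim 2 supplies only the 25%, the alpha and the claimed power.

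**Method.** Two-sample t-test. Standardised difference d = difference/SD; noncentrality = d/sqrt(1/n1 + 1/n2); degrees of freedom n1 + n2 - 2. Power comes from the noncentral t distribution.

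**Control check on section 14.** Difference = 0.1 - (-0.5) = 0.6; d = 0.6/0.25 = 2.4; noncentrality = 2.4/sqrt(2/12) = 5.88. Power is 99.99%, so section 14's statement of more than 90% reproduces. The method and the reading of the SD are therefore consistent with the protocol.

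**Aim 2, 25% of the XN change.** 0.25 x 0.5 = 0.125 pg/ml; d = 0.125/0.25 = 0.5.

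**Aim 2, 25% of the net effect.** 0.25 x 0.6 = 0.15 pg/ml; d = 0.15/0.25 = 0.6.

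The document does not give the Phase 1 group size or the SD in healthy adults. The table therefore assumes SD 0.25 in both populations and varies the group size.

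| Phase 1 group | d = 0.5, 12 on XN | d = 0.5, 16 on XN | d = 0.6, 12 on XN | d = 0.6, 16 on XN |
|---|---|---|---|---|
| Same size as XN arm | 21.6% | 27.8% | 29.0% | 37.6% |
| 32 | 30.3% | 35.9% | 41.0% | 48.4% |
| 64 | 34.8% | 42.4% | 46.9% | 56.4% |
| 1,000 | 40.5% | 50.9% | 54.2% | 66.2% |
| Effectively unlimited | 41.0% | 51.6% | 54.7% | 67.0% |

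**Size needed.** At d = 0.5 with equal groups, 80% power needs 64 per group.

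**Detectable difference.** At 12 per group, 80% power needs d = 1.197, which is 1.197 x 0.25 = 0.30 pg/ml, or 0.30/0.5 = 60% of the XN change. At 16 per group it needs d of about 1.025, which is 0.256 pg/ml, or about 51%.

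**More generous readings.**
- One-sided test, d = 0.5, equal groups: 32.4% (12) and 39.6% (16).
- One-sided, d = 0.6, all 16 retained, unlimited Phase 1 group: noncentrality 0.6 x sqrt(16) = 2.4, less 1.645 = 0.755, giving about 77.5%.
- The figure of 24 per arm printed at the end of section 14 cannot arise from 32 randomised. Taken at face value with equal groups and d = 0.5, it gives 39.6%.
- Reading 25% as 0.25 pg/ml (d = 1): 64.9% at 12 and 78.1% at 16 (80.7% by normal approximation). That is 0.25/0.5 = a 50% difference, and the higher figure ignores attrition.

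No reading of 25% as a relative difference reaches 80% with 12 to 16 participants on XN.

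**The case against.** **True power unknown.** A reader might infer that the protocol's own figures put Aim 2's power at 22-28%. They do not. Section 14 describes XN versus placebo within Crohn's disease. The 22-28% also needs a Phase 1 group of 12-16, SD 0.25 in healthy adults, and -0.5 pg/ml as the base for the 25%. None of these is stated for this contrast, and the base may have been the healthy adults' change, which is not given. This objection stands, and it is why the result is given as a range.

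**Percentage points.** The 25% might mean 25 percentage points of change from baseline. At 12 versus 12 the needed 0.30 pg/ml would then be reached if baseline TNF-alpha were about 0.30/0.25 = 1.2 pg/ml or more. Baseline is not given, so this reading can be neither confirmed nor excluded.

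**Calprotectin.** It has no mean or SD anywhere in the protocol, so its power cannot be checked in either direction.

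**Efficacy analysis.** A reader might infer that all of Aim 2 rests on contrasts that cannot attribute a change to XN. For the cytokines that is wrong: section 14 powers XN versus placebo for TNF-alpha, and section 20a makes that comparison the principal one.

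**CDAI.** A reader might also infer an uncontrolled before-after analysis, biased by regression to the mean because entry requires CDAI above 150. Aim 2 does not exclude a comparison between arms. Table 2 also schedules CDAI again at Week 0 after both screenings, which lessens the effect of selection. What remains is a gap in wording.

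**Weight.** Aim 2 is secondary, section 20a calls the cytokine results preliminary, and the sample size is set in section 14. These points limit the consequence but do not make the power statement correct.

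**Conclusion.** The power sentence in Aim 2 is unsupported as written and should be corrected. Its figure has no stated inputs and does not reproduce from the only marker figures in the protocol. With SD 0.25 in both populations and a 25% relative difference, two-sided power is about 22-28% for a Phase 1 group of 12-16. It cannot exceed about 41-52% however large that group was, or about 55-67% on the net 0.6 pg/ml effect. These figures rest on TNF-alpha alone. If 0.25 were a standard error, the SD would be larger and power lower still.

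The sentence also attaches power to a non-randomised comparison across trials, which does not match the contrast in sections 8, 14 and 20a. The fault lies in the stated claim. Section 14's TNF-alpha calculation and the planned cytokine analysis are not called into question by it.

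**What to change.** 1. Delete the power sentence in section 7, Aim 2, or replace it with power for XN versus placebo in this trial. At 12 per arm, two-sided alpha 0.05 gives 80% power only for a standardised difference of about 1.2. Section 14's TNF-alpha scenario (2.4 SD) can be cited, since its figure reproduces.
2. Label the comparison with the Phase 1 healthy adults as descriptive.
3. State in Aim 2 that changes in fecal calprotectin and CDAI from baseline to week 8 are compared between XN and placebo, as section 20a already does for the cytokines.
4. If the sponsor wishes to keep a powered Phase 1 comparison, give its inputs: the base for the 25%, the SD in each population, the Phase 1 group size and the sidedness.

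The cost is an edit to the wording of section 7. Sample size, visits and procedures do not change. The stated power becomes less favourable.

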The recently completed Phase 1 of XN at NUNM resulted no statistically significant differences in any mean laboratory values between XN vs. placebo groups at Closeout/Week 8 (all p values>0.10). At Closeout/Week 8, 2 laboratory parameters met halting criteria in Group B, including 1 mild anemia and 1 AST elevation. Notably, all lab abnormalities present at Closeout/Week 8 were resolved upon re-testing. There were no statistically significant differences in the frequency of any laboratory abnormalities between groups, at any timepoint in the trial (pvalues all>0.2). No participants discontinued their study intervention due to AEs. There were no "Grade 3/Severe" or FDA Serious AEs reported in either group. There were no apparent trends in incident AEs in either group over the time course of the trial. Additionally, investigators previously evaluated the effect of 12.5 mg per day of xanthohumol within a formula in adults with IBD, including Crohn's disease. Complete blood count and comprehensive metabolic panel data indicated no adverse changes; mean values were within normal laboratory reference ranges at all time points. All adverse events were non-serious and most were related to preexisting symptoms.¹⁵

There are no known toxicities for human subjects taking oral supplements containing XN. The general population is primarily exposed to XN through consumption of beer. A major brand beer contains about 0.5-1 mg prenylflavonoids (mainly XN and iso-XN) per liter and a bitter microbrew ale may contain as much as 4 mg of total prenylflavonoids.¹⁶ In Europe, a beer/beverage, containing 4 mg of XN per liter, has been on the market for several years without adverse effects having been reported by the consumers. Based on the available human data and the results from the above cited animal studies, we expect that the study participants will not develop adverse effects at the proposed dosage regimens during the 8-week exposure period.

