We aim to extend our preliminary findings related to potential application of XN as a therapeutic by testing its effects in a sample of human adults with CD. We will recruit 32 participants with CD, and randomize them to either 24 mg of XN plus rice protein, or a rice protein placebo for 8 weeks. The study drug will be identical to the preparation used in the Phase 1 trial that preceded this Phase 2 protocol, i.e., XN will be administered as 24 mg of a 99+% pure raw material provided by Hopsteiner USA (NY) combined with 288 mg of rice protein (California Natural Products, Lathrop, CA), 109.3 mg microcrystalline cellulose (Stauber USA, Fullerton, CA), 4.3 mg Aerosil®

Protocol

200 fumed silica (Vivion Inc., San Carlos, CA), and 4.3 mg magnesium stearate (Nitika Pharmaceutical Specialties, Maharashtra, India), and formulated into a capsule by Metagenics, Inc. (Gig Harbor, WA). XN has been combined with a rice protein carrier due to improved bioavailability.⁹

Our *primary working hypothesis* is that XN at the given dose will be safe and tolerable in adults with active CD. We will test this hypothesis by collecting blood samples at screening, baseline, and every two weeks to monitor changes in laboratory values including liver enzymes, renal function markers, and hematological markers. We anticipate very low frequency of treatment discontinuation due to adverse effects.

Our *working hypotheses* of Aims 2, 3, and the Exploratory Aim are that XN and its microbiotaderived metabolites may reduce inflammation and reduce biomarkers of barrier permeability in the inflamed gut. In order to test this hypothesis, we will collect blood, urine, and stool samples at baseline and every two weeks to monitor gut microbiome profiles and measure XN metabolite profiles. We will also measure fecal metabolome (including bile acid profiles) and lipidome profiles, as well as established fecal and plasma indicators of IBD severity, including fecal calprotectin and C-reactive protein. Because the actions of XN and its metabolites target specific abnormalities in CD, we hypothesize that the proposed studies will deliver a mechanism-based biological signature of XN exposure and its effect on CD mitigation.

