- Malignancy within the last 5 years (with the exception of basal cell carcinoma, squamous cell carcinoma, and/or carcinoma in situ of the cervix)
- Women who are lactating, pregnant or planning pregnancy within the next four months
- Typical intake of more than 2 alcohol-containing beverages per day, more than 14 per week, or more than 4 in any single day within the past 14 days.
- Smoking tobacco or use of nicotine products Use of illicit drugs/substances (such as but not limited to cocaine, phencyclidine (PCP), and methamphetamine) within 14 days of screening
- Use of inhaled or ingested *Cannabis* products, including CBD
- Currently participating in another interventional research study, or participated in another interventional research study within 14 days of screening
- Do not have a medical provider available to consult with and/or manage medications for their CD as needed
- Received a vaccination within 14 days prior to clinical screening.

Candidates will be given the option to stabilize or eliminate alcohol intake, allowable dietary supplement and medication intake, exercise, and diet to the requirement stated above for 14 days, and/or eliminate cannabis use and illicit substance and may re-contact the study team after.

11a Interventions

The intervention is XN (24 mg/day plus 288 mg of rice protein plus 117.9 mg of excipients) or placebo (rice protein 288 mg/day plus 117.9 mg of excipients) taken by mouth once daily for 8 weeks.

11b Withdraw/Discontinuation

A participant may elect to withdraw from the trial at any time they choose, if they experience AEs or for no stated reason. However, participants will be actively withdrawn if they demonstrate new onset, moderately severe gastrointestinal AEs, attributable to the intervention. Participants will also be withdrawn if they have any *critical* value return on routine clinical laboratory measures of safety, including changes in blood counts, liver function tests and/or renal function tests.

Safety measures include self-reported adverse events, % new abnormal and mean changes in specified clinical laboratory parameters including red blood cell count, ALT, AST, GGT, bilirubin, alkaline phosphatase eGFR, and BUN: creatinine ratio.

11c Adherence

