A Data Safety and Monitoring Board (DSMB) independent of the study team will be created for the proposed trial and will consist of: a clinical investigator with IBD experience, a clinician with IBD practice experience, a biostatistician, and at least one other experienced clinical researcher/trialist. The DSMP will review all AE reports according to IRB policy, monthly reports of recruitment, retention and overall study progress; and attend quarterly meetings. Protocol amendments can be suggested by members of the independent monitoring committee at any time, and additional meetings of the DSMB can be called by any member at any time. The PI and study coordinator will also participate in quarterly meetings with the committee to provide additional information and/or clarify reports.

21b This study will be stopped prior to its completion if the intervention is associated with adverse effects that call into question the safety of the intervention, if any new information becomes

Protocol

available during the trial that necessitates stopping the trial; or if other situations occur that might warrant stopping the trial. The ultimate decision to stop the trial may be made by the DSMB, NCCIH, and/or the FDA.

The trial will be halted if >25% of the total sample experience moderate or greater AEs or laboratory abnormalities requiring them to withdraw.

The DSMB will provide a final recommendation to the PI to halt the study or amend the study protocol, and will develop a response plan, in consultation with the NUNM IRB and the NCCIH Program Officer.

If immediate changes are required for participant safety, enrollment and other study activities will not continue until the modifications/amendment is approved by the IRB.

22 Harms

Adverse Event Monitoring and Reporting

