The PI will have final responsibility for all reporting to the NUNM IRB, DSMB and/or NCCIH PO as required.

Clinical Management Plan/ Plans for Ensuring Necessary Medical Intervention

Participant safety is of the greatest concern in clinical trials of experimental compounds, even when naturally derived and available in food. Of particular concern is any threat to the clinical stability of a person with CD. For this reason, with their consent, we will notify participant's primary care and/or medical specialist of their patient's participation in the trial. We will inform their medical providers should it become necessary to communicate with them about any laboratory abnormalities, critical values and/or AEs should they be discovered at baseline or throughout the clinical trial.

We will maintain the ability to administer additional blood-based or stool-based testing for acute or viral infection as circumstances require.

Potential Risks to Participants

Risks associated with any dietary supplement include gastrointestinal symptoms such as gas, bloating, digestive upset and change in bowel movement frequency or consistency. Also, there is a chance of identifying a previously unknown allergy, and therefore a risk of rash, breathing difficulty and serious allergic reaction.

We will ask about symptoms at each study visit and any side effects will be recorded. We may ask the participant to discontinue the study product if we believe it would be in their best interest.

There will be six blood draws during this study. There is a small chance that the needle will cause some discomfort, bruising, redness or bleeding at the needle puncture site. Occasionally, individuals may feel lightheaded or faint during or immediately after a blood sample is collected. There is a rare risk of swelling around the vein or of infection.

We will do everything we can to keep records private, yet there is always a small risk of a breach of confidentiality of personal health information. These risks have been addressed and minimized as much as is possible by keeping data in locked cabinets and on password protected and encrypted computers, and by using ID numbers instead of names on all data collected.

There is a chance that some participants may confuse research study visits for routine clinical care. **Protocol** Study Title: Xanthohumol Microbiome and Signature in Crohn's Disease (XMaS in Crohn's) Trial

23 Auditing

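### Section 11b appears to take participants with attributable GI events or critical labs out of the trial, so their later visits are lost; the effect is probably small and the fix is cheap

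*Protocol*

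**What the plan says.** Section 11b opens with voluntary withdrawal: "A participant may elect to withdraw from the trial at any time they choose". The next sentence makes it compulsory in one situation: "participants will be actively withdrawn if they demonstrate new onset, moderately severe gastrointestinal AEs, attributable to the intervention". The one after adds any critical value on the routine safety labs. Neither sentence says what the participant is withdrawn from.

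Stopping the product alone is worded separately, and as an option, in section 22 (Potential Risks to Participants): "We may ask the participant to discontinue the study product if we believe it would be in their best interest". The halting rule in section 21b counts "moderate or greater AEs or laboratory abnormalities requiring them to withdraw".

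On follow-up, section 13b sets remote procedures for missed visits and institute closure only. Section 30 follows adverse events to resolution or stabilisation. Section 20a compares the percentage newly abnormal between arms at every two-week visit, tests mean changes and trends in the labs, and makes baseline to week 8 the main biomarker comparison.

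**The concern.** The participants removed are by rule those with a critical lab or an attributable GI reaction, so their missing later visits depend on the outcome. Loose stools and abdominal pain are also weighted CDAI items (section 18a), which ties the GI trigger directly to a secondary outcome.

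If triggers fall mainly in the XN arm and the toxicity persists after product is stopped, the later lab tables and week-8 comparisons make XN look safer than it is. They also look nearly the same whether toxicity resolves or persists, a distinction a safety trial should be able to show by arm.

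**Working it through.** **Reading the text.** The first sentence of 11b names the trial as the object. The compulsory sentences follow directly and give no new object. Where the protocol means product only, as in section 22, it says so. Sections 13b and 30 do not fill the gap: the first covers other situations, and the second follows the event, not the scheduled panel, stool, cytokines or CDAI.

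**The plan's own figure.** Section 14 allows 25% attrition from 32 randomised: 24 / (1 − 0.25) = 32, leaving 12 per arm. This reproduces and is not affected by the point.

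**How many are affected.**
- Section 6a on Phase 1: "No participants discontinued their study intervention due to AEs". For this trial: "We anticipate very low frequency of treatment discontinuation due to adverse effects".
- Section 14 on attrition: "though we had <10% attrition in our previous trial in this population". Ten percent of 32 is about 3 participants over both arms.
- Working range (assumption): k = 0 to 2 affected XN participants, none on placebo.
- The chance of at least one trigger among 16 XN participants, 1 − (1 − q)^16, is 28%, 56% and 82% for assumed rates q of 2%, 5% and 10%.

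**Model (assumptions).** There are 16 per arm. Onset is at week 2, 4, 6 or 8 with probability 1/4 each. The triggering value is kept and later values are missing. The marker rises by r SD. Let m ~ Bin(k, 1/4) be the number of affected participants who still have a week-8 value.
- As written: E[r·m / (16 − k + m)]
- Followed, resolved by the next visit: r·(k/4) / 16
- Followed, persists: r·k / 16

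With r = 3:
- k = 1, as written: 0.25 × 3/16 = 0.047. Resolves: 0.047. Persists: 0.188.
- k = 2, as written: 0.375 × 3/15 + 0.0625 × 6/16 = 0.075 + 0.023 = 0.098. Resolves: 0.094. Persists: 0.375.

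The same formulas with r = 1 as an indicator give the percentage newly abnormal, taking all participants as normal at baseline. For CDAI, assume 2 more loose stools and 1 more pain grade a day: 2 × 2 × 7 + 5 × 1 × 7 = 63 points.

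| Week-8 quantity | Affected | As written | Followed, resolves | Followed, persists | Gap if it persists |
|---|---|---|---|---|---|
| Mean difference, 3-SD rise | 1 | 0.047 SD | 0.047 SD | 0.188 SD | 0.141 SD |
| Mean difference, 3-SD rise | 2, same marker | 0.098 SD | 0.094 SD | 0.375 SD | 0.277 SD |
| % newly abnormal in XN | 1 | 1.6 | 1.6 | 6.3 | 4.7 points |
| % newly abnormal in XN | 2, same parameter | 3.3 | 3.1 | 12.5 | 9.2 points |
| CDAI mean (points) | 1 | 1.0 | 1.0 | 3.9 | 3.0 |
| CDAI mean (points) | 2 | 2.1 | 2.0 | 7.9 | 5.8 |

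**Scale.** The standard error of a week-8 mean difference is √(2/16) = 0.354 SD, so the largest gaps are 0.141/0.354 = 0.4 and 0.277/0.354 = 0.8 standard errors. If two are withdrawn and only one carries the marker, the gap is 0.138 SD. With a 1-SD rise the gaps are 0.047 and 0.092 SD.

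**Data lost.** Visits missed are 3, 2, 1 or 0, an average of 1.5 of the 4 after baseline. A week-8 value is lost with probability 3/4, so 0.75 to 1.5 of 16 values (5 to 9%) for one or two affected.

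**The case against.** The strongest reply is that the reading is an inference. The heading of 11b also covers discontinuation, no sentence ends visits, and Table 2 discharges participants only at week 8. The ambiguity is real, but coordinators could apply the rule either way, and the more natural reading is the one that loses data.

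Second, much is already covered. The triggering event counts in the Aim 1 hypothesis and the halting rule, adverse events are followed to resolution, and the mixed models keep values from before withdrawal. All of this stands. Whether an individual's event resolved will be known. It will not appear in the scheduled between-arm comparisons, because event follow-up does not supply those measurements.

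Third, the size. Phase 1 favours the benign case, since "all lab abnormalities present at Closeout/Week 8 were resolved upon re-testing", though Aim 2 describes those participants as healthy adults. Section 6a also reports only non-serious events with a lower XN dose in adults with IBD. The larger gaps need a big rise, full persistence off product and every trigger in XN. Because attribution is masked, placebo participants with active disease could also meet the GI trigger and narrow the difference. With one other abnormal participant per arm, Fisher's test gives p = 1.0 whether one persistently abnormal XN participant is omitted or kept. For two, it gives 1.0 against 0.60. This stands, and it is why the point is not a major one.

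Finally, the missing-data method may sit in an analysis plan, but a plan cannot supply samples that were not taken.

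**Conclusion.** The concern holds. As written, section 11b most naturally ends scheduled assessments for participants with the events a safety trial most wants to follow, and no other section restores them. The primary participant-level count is unaffected.

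The bias in later-visit and week-8 comparisons is about 0 if toxicity resolves on stopping product. It is at most 0.14 to 0.28 SD, or 3 to 6 CDAI points, if toxicity fully persists, which is under one standard error. These figures rest on assumed values: 0 to 2 affected participants, all in XN; even onset over weeks 2 to 8; a 3-SD rise or 63 CDAI points. The protocol gives no withdrawal rate for these triggers. The change is worth making because it is cheap, not because a large bias is expected.

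**What to change.** Keep both triggers in 11b but change their consequence. Suggested wording:

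*Participants meeting these criteria will permanently stop study product. Where medically appropriate, they will be asked to continue scheduled visits, labs, CDAI and samples to week 8, remotely under 13b if needed, and will be analysed in their randomised arm. Only withdrawal of consent ends follow-up.*

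In 21b, count events that require a permanent stop of study product under 11b. The halting rule then still includes these participants and does not pick up the discretionary stops of section 22. Align the consent form.

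**Cost.** Sample size is unchanged. Each affected participant attends about 1.5 more visits: 1.5 × 190 = 285 dollars, within the planned stipend of 50 + 5 × 190 = 1,000 dollars (section 15). The wording change goes through the amendment route of section 25.

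**Downside.** For these few participants, week-8 values reflect assignment and not continuous exposure, possibly with emergency glucocorticoids (section 11d). Off-product samples add little to the XN metabolite aims.
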